16.2.2.2 Urine

As to the derived PD urine variables, descriptive statistics (n, arithmetic mean, SD, median, min, and max) will be used to summarize by study part, cohort (for Part C) and scheduled timepoint. For 24-hour urine calcium, 24-hour urine phosphate and 24-hour urine magnesium (for Part C only), descriptive statistics will also be provided for change from baseline.

In addition, linear plots will be provided for bone turnover biomarkers, in a way similarly as the linear plots mentioned above for main PD analysis.

16.2.2.3 Standard of Care

Summary and frequency table will be provided for each variable of standard of care by cohort at baseline, at day 14, at the end of main treatment period and every two weeks during extension.

Dosing amounts of supplements prescribed by investigators will be listed and used for the analysis of standard of care.

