Serum calcium and phosphate blood samples will also be taken on Day 3 (±1 day), Day 5 (±1 day), Day 8 (±1 day), Day 11 (±1 day), Day 21 (±1 day), and Day 30. In addition, there may be additional and unscheduled checks for serum calcium and phosphate at the discretion of the Investigator. After the last study drug administration, if subjects are not entering the extension period, they will be instructed to resume their prestudy calcium and active vitamin D treatment regimen and doses based on assessments performed on Day 28/ET to Day 30.

Extension Phase

Extension phase will start immediately following Day 28 visit. On Days 29 onwards, patients will continue on the same dose of AZP-3601 as on Day 28, then individual titration of AZP-3601 may start as early as Day 30.

Patients will return to the clinical site for additional visits on Day 56 (±4 day), Day 84/ET (±4 day), and Day 85 (Day 84 + 1 day).

Serum calcium and phosphate blood samples will also be taken on Day 42 (±4 day), Day 70 (±4 day), and Day 86 (Day 84 + 2 days). In addition, there may be additional and unscheduled checks for serum calcium and phosphate at the discretion of the Investigator.

Patients will have their serum calcium/albumin levels measured within 5 days after any adjustment of AZP-3601 or any other time at the discretion of the investigator. The investigator will be free to perform any serum or urine test if needed.

After the last study drug administration, the patients will be instructed to resume their prestudy calcium and active vitamin D treatment regimen and doses based on assessments performed on Day 84 (\pm 4 day) to Day 86 (Day 84 + 2 days).

Follow-up

on Day 37 (±2 days). For patients entering the extension phase, follow-up visit will be on Day 98 (±4 days)

* For each study part, the planned treatment period, day of discharge, and follow-up period may be adapted depending on emerging study results.

Subjects/Patients

: Approximately 24 male or female subjects with HP who are on treatment with oral calcium and active vitamin D

Diagnosis and Main Criteria for Inclusion

	- within the normal range of the laboratory under standard of care
	If historical laboratory analysis (≥12 months) is not available, an additional
	recent concomitant laboratory measurement is required (with a minimum of
	3 weeks testing interval).
	- Requirement for therapy with calcitriol ≥0.25 µg per day or alphacalcidol
	≥0.50 µg per day (both are active vitamin D supplements), and requirement

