-	Bone turnover biomarkers (serum bone-specific alkaline phosphatase [BSAP], serum carboxy-terminal telopeptide of type I collagen [s-CTx], serum procollagen type 1 amino-terminal propeptide [P1NP], and serum osteocalcin).
-	Serum magnesium.
-	Serum 25-hydroxy vitamin D and serum 1,25-dihydroxy vitamin D.
P	art C only:
-	Reduction in daily dose of calcium and active vitamin D supplementation
	(number of patients achieving a reduction of 50% and more in daily doses of calcium and active vitamin D supplementation at the end of the treatment period will be calculated).
-	EQ-5D questionnaire and short form health survey 36 (SF-36) questionnaire. Bone mineral density as assessed by DXA
* The timing, type, and number	er of safety, PK, PD, and additional assessments may be changed during the

study depending on emerging study results.

Statistical Methods	
Sample Size Calculation	: The sample size and design for each part is based on the desire to obtain adequate safety, tolerability, PK, and PD data to achieve the objectives of the study while exposing as few subjects as possible to the investigational product and study procedures. This sample is typical for a FIH study. Any p-values to be calculated according to the statistical analysis plan will be interpreted in the perspective of the exploratory character of this study.
Safety	: Descriptive statistics
РК	: Descriptive statistics for all relevant PK parameters: n, mean, SD, minimum, median, maximum, geometric mean, and CV%; analysis of variance on C_{max} and AUC parameters to determine dose-proportionality
PD and Additional	: Descriptive statistics.

in the statistical analysis plan.

Further details will be provided

Table 3 Schedule of Assessments – Part C (MAD Part in Patients with HP – Main Treatment Period)

Assessment		Scre	ening/0	Optimiz	ation				Ν	lain Tr	eatmen	t Perio	d (4 we	eeks tr	eatmer	nt)			Follow-up
(Week) Day	(-8)	(-6) a,b	(-4) a,b	(-2) _{a,b}	-4 ^b	-1	1	3 ^b	5 ^b	8 ^b	11 ^b	14	15	16	21 b	28/ ET	29	30 b	37
Visit Window (days)	±2	±2	±2	±2	±1			±1	±1	±1	±1				±1				±2
Informed Consent	Х															X p			
Medical History	Х																		
Demography	Х																		
Dispensing and Training of Diary							Х												
Completion of Diary							Х	Х	Х	Х	Х	Х	Х	Х	Х	Х	Х	Х	Х
Physical Examination ^c	F						Α					Α		Α		F	Α		A
Body Weight and Height	Х															X d			
Serum Pregnancy Test (Females of childbearing potential Only)	x					х						х				х			

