8.1.2 Imputation

Unless otherwise noted, data will not be imputed. Exceptions are missing start and end times of adverse events (AEs), see Section 17.1.1, PK concentrations below lower limit of quantification (LLOQ), see Section 15.2, PTH(1-84) concentrations below LLOQ, see Section 16.2.2.1, and missing score in SF-36 Questionnaire, see section 16.1.5.

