8.1.3 Descriptive Statistics

Unless otherwise indicated, continuous variables will be summarized with the following descriptive statistics: number of observations (n), (arithmetic) mean, SD, minimum (min) value, median, and maximum (max) value. For PK data, geometric mean and geometric CV will be presented in addition.

• Geometric mean = exp(m), where m is the arithmetic mean of the log-transformed data.

EDSREP 009 T 01 G Page 13 of 53

Version Date: 26-Aug-2022

Geometric CV (%): sqrt(exp(s*s)-1)*100, where s*s is the variance of the log-transformed data.

Categorical data will be summarized with frequencies and percentages. Percentages by categories will be based on the number of subjects exposed within a treatment.

For categorical data, the categories will be presented in the tables exactly as they appear in the electronic case report form (eCRF) / Database. No data manipulation will be done for presentation purposes.

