16.1.3 Standard of Care

Part C only:

Standard of care will be evaluated at Baseline, at Day 14, at the end of the main treatment period (Day 28) and after 2 weeks during the extension period.

Variables for Standard of Care includes the following:

- Mean active vitamin D dose
- Mean calcium dose
- Number of patients
 - Taking neither vitamin D nor calcium
 - \circ Taking no vitamin D and \leq 1000 mg/day of calcium
 - o Taking no vitamin D and ≤500 mg/day of calcium
 - Taking no vitamin D
 - Taking no calcium
 - o Taking ≤500 mg/day of calcium
 - o Taking ≤1000 mg/day of calcium

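### Supplement doses are reported only as visit means, with no within-patient change, and the SAP leaves out the protocol's count of patients with at least a 50% reduction without recording it

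*SAP*

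**What the plan says.** - SAP 16.1.3 lists nine standard-of-care variables for Part C. Two are continuous, "Mean active vitamin D dose" and "Mean calcium dose". The other seven count patients at set supplement levels, including the treatment goal (active vitamin D stopped and calcium no higher than 500 mg/day).
- SAP 16.2.2.3 tabulates them: "Summary and frequency table will be provided for each variable of standard of care by cohort at baseline", then at Day 14, at the end of the main period and during the extension. The data source is stated: "Dosing amounts of supplements prescribed by investigators will be listed and used for the analysis of standard of care".
- SAP 8.1.2: "Unless otherwise noted, data will not be imputed". Supplement dose is not among the exceptions.
- SAP 8.1.3, on categorical data: "Percentages by categories will be based on the number of subjects exposed within a treatment".
- Change from baseline is specified in SAP 16.2.1 (main serum variables), 16.2.2.2 (24-hour urine calcium, phosphate and magnesium), 16.2.2.4 (EQ-5D and SF-36) and 16.2.2.5 (DXA), but not for supplement doses.
- The protocol synopsis, under PD and other variables, plans a within-patient measure at the end of treatment: the "number of patients achieving a reduction of 50% and more in daily doses of calcium and active vitamin D supplementation". It is not in SAP 16.1.3, and SAP 7.1 (Changes from Protocol) does not mention it. SAP 3.0 says that substantial differences from the protocol will be identified.
- The extension is offered only to patients who complete the 4-week main period, and it needs separate consent.

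**The concern.** Supplement reduction is built into the secondary PD objective and into the titration aims of the extension. A reader will judge it by setting a later mean dose beside the baseline mean. That comparison is clean only if both means cover the same patients. With no imputation, a patient without a dose record at a visit is absent from that visit's mean. The extension means can cover only patients who finished Day 28 and agreed to continue. In cohorts of about 12, two or three absences can shift a mean noticeably.

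The measure that would have avoided this, a per-patient reduction, exists in the protocol but not in the SAP's variable list.

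**Working it through.** The plan states no sample-size calculation, dropout rate or expected dose, so there is no figure to reproduce. The check is algebra with assumed doses.

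**Inputs.** From the documents: n = 12 per cohort (approximate), entry calcium of at least 1000 mg/day, goal of at most 500 mg/day. Assumed: k = 1 to 4 patients leave, and all mean doses below.

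**Notation.** Bd is the baseline mean of those who leave, Bc the baseline mean of those who stay, and Fc the later mean of those who stay.

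1. Difference of visit means = [(n−k)Bc + k·Bd]/n − Fc.
2. Paired reduction in those who stay = Bc − Fc.
3. Step 1 minus step 2 = (k/n)(Bd − Bc). This is the baseline-mix error, and it takes the sign of Bd − Bc.

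**Same table, different truths** (n = 12, k = 2, Fc = 250 mg/day). In every row the baseline mean of all 12 is 2000 and the difference of visit means is 1750 mg/day.

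| Bd | Bc | Paired reduction | Visit means minus paired | Paired, % of own baseline |
|---|---|---|---|---|
| 3000 | 1800 | 1550 | +200 | 86.1% |
| 2000 | 2000 | 1750 | 0 | 87.5% |
| 1000 | 2200 | 1950 | −200 | 88.6% |

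When those who stay come close to stopping supplements, the mix moves the milligram figure much more than the percentage. It matters more when the true reduction is small.

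**No true reduction.** Take 12 baseline doses evenly spaced from 1000 to 3000 mg/day (mean 2000), with nobody changing dose and 3 leaving.
- The 3 highest leave: the mean becomes 1727, and (2000 − 1727)/2000 is an apparent 13.6% reduction.
- The 3 lowest leave: the mean becomes 2273, an apparent 13.6% increase.

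**A different target: all treated patients, with leavers counted as having no reduction.** This equals (n−k)(Bc − Fc)/n, and the gap to the visit means is (k/n)(Bd − Fc). With Bd = Bc = 1000 and Fc = 500, the visit means show 500 mg/day. The all-treated figure is 458, 417, 375 and 333 mg/day for k = 1 to 4, about 42 mg/day (500/12) less per leaver. The gap is zero if nobody leaves. It sizes a sensitivity summary; it does not measure an error in the planned table.

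**The counts.** If 8 of 12 reach a goal and 2 leave, the exposed denominator gives 8/12 = 66.7%. A remaining-patients denominator would give 8/10 = 80.0%. The SAP's rule is the more cautious one.

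**The case against.** The strongest case for the plan runs as follows.

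- Seven of the nine variables are counts, and their percentages use patients exposed. If that means all treated patients, leavers already count as not reaching the goal. This stands, although the SAP does not say whether exposed in the extension means all treated patients or only those who entered.
- The default statistics in SAP 8.1.3 include n, and individual prescribed doses are listed, so a reader could work out paired changes by hand. This is true, but the reader should not have to, and n alone does not give the baseline mean of the patients who remain.
- The study is single-arm and descriptive, with no formal testing. This limits the consequence, but a descriptive mean is still affected by who is in it.
- Exclusion of leavers is inferred from the no-imputation rule. Tables 3 and 4 of the protocol label visits 28/ET and 84/Early termination, so an early-termination dose might be used. The SAP does not say, which is part of the point.

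A reader might go further and infer that leavers, told to "the patients will be instructed to resume their prestudy calcium and active vitamin D treatment regimen and doses", drop out of the means, so that the reduction is overstated in the drug's favour. The documents do not support that. They give no leaving rate or reasons, and the baseline-mix error has no fixed sign. The protocol ties resumption to assessments around the last dose, so return to the old dose is not automatic. Prestudy dose is also not baseline dose, because up to 8 weeks of optimization come between them. Scoring everyone who leaves as zero reduction would also treat a patient who completed Day 28 and declined an optional extension as a failure.

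**Conclusion.** The concern holds in a limited form. Supplement dose has no specified within-patient change, unlike the other variables named above, and the protocol's per-patient reduction count is missing from the SAP's variable list without a record in section 7.1. The SAP's output list and table shells (Appendices 3 and 4) are not in the text available, so this rests on the variable definitions and the analysis text.

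The effect is zero if nobody leaves. Otherwise the baseline-mix part is (k/12)(Bd − Bc) in either direction: ±200 mg/day in the two unequal-baseline examples with 2 of 12 gone, and ±13.6% in the no-change example with 3 gone. All of these doses are assumptions. The direction is unknown in advance, so the plan cannot be called biased towards the drug. No error rate or power is affected.

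Paired change would remove the baseline-mix part only. It would still describe the patients who remained, and should be labelled so.

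**What to change.** In SAP 16.1.3 and 16.2.2.3:

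1. Add within-patient change and percent change from baseline in daily oral calcium and in active vitamin D at each listed time point. Define baseline as the last dose prescribed before the first AZP-3601 dose. Show n and the baseline mean of the same patients beside each result.
2. Restore the protocol's count of patients with at least a 50% reduction at the end of treatment, with all treated patients in the cohort as denominator. If it is dropped on purpose, say so in section 7.1.
3. State how early-termination doses and doses after stopping AZP-3601 enter the tables, and what exposed means for extension percentages.
4. Reconcile the extension time points: 16.1.3 reads as a single evaluation two weeks in, 16.2.2.3 as one every two weeks.

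An all-treated summary that counts patients who discontinued AZP-3601 as having no reduction may be added as a labelled sensitivity summary, not as the main result. It should not count patients who completed Day 28 and declined the extension as failures of the main period.

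The cost is SAP wording and one derivation from doses already collected. The paired figures may come out lower or higher than the difference of visit means. With leavers, the sensitivity summary would probably be less favourable.

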16.2.2.4 EQ-5D and SF-36

Descriptive statistics (n, arithmetic mean, SD, median, min, and max) will be used to summarize scores (absolute values and changes from baseline) for the parameters of these questionnaires by cohort at each scheduled day.

16.2.2.5 DXA Analysis

Descriptive statistics (n, arithmetic mean, SD, median, min, and max) will be used to summarize BMD and Trabecular Bone Score (absolute values and changes from baseline) by treatment dose level and at each scheduled day.

17.0 Safety Analyses

17.1 Safety Variables

The following safety variables will be summarized by study part (Part C main, or C extension) if applicable:

- AEs
- Injection Site Reaction
- Clinical Laboratory Evaluations
 - o Clinical Chemistry
 - Hematology
 - Coagulation
 - o Urinalysis
- Vital Signs
 - Systolic Blood Pressure
 - o Diastolic Blood Pressure
 - Pulse rate
 - Body temperature
- Electrocardiograms (ECG)
 - o Heart Rate
 - PR-Interval
 - o QRS-Duration
 - QT-Interval
 - QTc Friderica
- Part A only: Continuous cardiac monitoring (telemetry)
- Physical Examination
- Body Weight and BMI

EDSREP 009 T 01 G Page 30 of 53

Protocol: AZP-3601-CLI-001 Version Date: 26-Aug-2022

Antidrug antibodies (ADA) in plasma

17.1.1 Adverse Events

A treatment-emergent adverse event (TEAE) is defined as any event not present prior to (the first) administration of the study drug or any event already present that worsens in either severity or frequency following exposure to the study drug.

An overall summary table will be provided by treatment and overall for each study part with the number of subjects and events reporting, AEs, TEAEs, treatment-emergent SAEs, treatment-emergent AEs of special interest (AESIs), and TEAEs leading study drug discontinuation.

Based on the pharmacology of AZP-3601 as well as other PTH analogs, and the pathophysiology of HP, AESIs are as follows:

- Hypocalcemia (including the following symptoms: agitation, anxiety, hypoestesia, paresthesia, muscle cramping, muscle fatigue, musculoskeletal pain, musculoskeletal stiffness, myalgia, tetany, seizure, tremor, brain fog).
- Hypercalcemia (including the following symptoms: thirst, frequent urination, abdominal pain, nausea, vomiting, fatigue).
- Hypercalciuria.
- Orthostatic hypotension and vasodilatory symptoms (including postural/orthostatic dizziness, syncope, tachycardia/palpitations).

A summary table with the number of subjects reporting TEAEs and the number of events, categorized by system organ class (SOC) and preferred term (PT) coded according to the MedDRA, will be presented by /cohort (for Part C) and overall for each study part. Subjects will only be counted once within each system organ class or preferred term.

A summary table with the number of subjects reporting TEAEs, categorized by SOC, PT and relationship to study drug (Related or Not Related), will be provided by //cohort (for Part C) and overall for each study part. A treatment-related TEAE is defined as any TEAE that is assessed by the investigator as definitely, likely, possibly or unlikely related to study treatment. TEAE that is assessed as Not Related will be defined as not treatment-related. Subjects with multiple events within a particular body system or preferred term will be counted under the category of their most drug-related event within that body system or preferred term.

A summary table with the number of subjects reporting TEAEs, categorized by SOC, PT and severity as recorded on eCRF (Mild, Moderate, Severe, Life-threatening or Death), will also be provided by cohort (for Part C) and overall for each study part. Subjects with multiple events within a particular body system or preferred term will be counted under the category of their most severe event within that body system or preferred term.

A summary table with the number of subjects reporting treatment-emergent AESIs and the number of events, categorized by SOC and PT coded according to the MedDRA, will be presented by treatment (for Parts A and B)/cohort (for Part C) and overall per for each study part. Subjects will only be counted once within each body system or preferred term.

The following missing data will be imputed as defined (for calculations only / will not be presented):

- Missing AE severity or relationship will be assumed to be severe or related, respectively
- Missing AE start times for the determination of treatment emergence will be assumed to occur after treatment unless partial date documents the AE as happening prior to treatment
- Missing AE start date will be assumed to be after treatment for the determination of TEAE unless partial or complete end date documents the AE as happening prior to treatment

All AEs (including non-treatment-emergent events) recorded on the eCRF will be listed, with a flag to indicate whether the AEs are AESIs.

A separate listing of TEAEs leading to study drug discontinuation will be provided.

EDSREP 009 T 01 G Page 31 of 53

Protocol: AZP-3601-CLI-001 Version Date: 26-Aug-2022

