5.0 Study Objectives

5.1 Primary

•

- To assess the safety and tolerability of AZP-3601 following single and 4-week multiple ascending doses administered by sc injection to patients with hypoparathyroidism (HP) (Part C, Main Treatment Period)
- To assess the safety and tolerability of AZP-3601 during a 2-month treatment extension period (Part C, Extension Phase) in patients with HP

EDSREP 009 T 01 G Page 4 of 53

Protocol: AZP-3601-CLI-001 Version Date: 26-Aug-2022

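### The TEAE and AESI tables do not separate events on AZP-3601 from events after it is stopped and prestudy supplements are resumed

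*SAP*

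**What the plan says.** SAP 17.1.1 opens with "A treatment-emergent adverse event (TEAE) is defined as any event not present prior to (the first) administration of the study drug" and adds "any event already present that worsens in either severity or frequency following exposure to the study drug". Both clauses look back to the first dose or to exposure, and neither has an upper limit. The imputation rules for missing AE dates in the same section address only whether an event came before treatment.

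The same section introduces the events of special interest with "Based on the pharmacology of AZP-3601 as well as other PTH analogs, and the pathophysiology of HP, AESIs are as follows". The list includes hypocalcemia, hypercalcemia and hypercalciuria. It then plans "A summary table with the number of subjects reporting treatment-emergent AESIs and the number of events, categorized by SOC and PT", by cohort and overall for each study part. SAP 17.1 gives two Part C periods for safety summaries, main and extension, and no follow-up period.

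Protocol Tables 3 and 4 mark AE monitoring after the last dose: on Days 29, 30 and 37 for patients who do not continue, and on Days 85, 86 and 98 for those who do. The synopsis (Follow-up) states "For patients entering the extension phase, follow-up visit will be on Day 98 (±4 days"). For the extension, Study Schedule says "After the last study drug administration, the patients will be instructed to resume their prestudy calcium and active vitamin D treatment regimen". It gives an equivalent instruction for patients who stop at Day 28.

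One primary objective in SAP 5.1 is "To assess the safety and tolerability of AZP-3601 during a 2-month treatment extension period (Part C, Extension Phase) in patients with HP".

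**The concern.** An open-ended TEAE window is often harmless. Here the end of dosing coincides with a planned reversal of background therapy. Supplements have been reduced or eliminated on AZP-3601; the drug then stops and the prestudy regimen returns. Hypocalcemia could follow loss of the drug, and hypercalcemia or hypercalciuria could follow the return of supplements. These are also the events through which the drug's own safety is judged.

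The objective concerns safety during a treatment period, but the count that serves it runs past that period. An AESI rate read from the tables would describe neither safety on the drug nor safety on stopping it.

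**Working it through.** There is no sample size or power figure to reproduce, because SAP 6.1 says no formal calculation was done. The check is day arithmetic and a reading of the other planned outputs.

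**Inputs**
- Main dosing: Days 1 to 28 (SAP 6.0).
- Extension dosing: 56 days from Day 29 (Protocol synopsis, Extension Phase), so the last dose is on Day 29 + 56 − 1 = 84, which matches the Day 84 visit.
- Follow-up: Day 37 (±2) without the extension, Day 98 (±4) with it.
- Cohort size: about 12, with up to two cohorts.

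**Off-drug share of AE-collection days** = off-drug days / (on-drug + off-drug days)
- No extension: 37 − 28 = 9; 9/37 = 24.3%. With the visit window: 7/35 = 20.0% to 11/39 = 28.2%.
- Extension part, Days 29 to 98: 98 − 84 = 14; 14/70 = 20.0%. If the Day 84 and Day 98 windows vary independently: 6/66 = 9.1% to 22/74 = 29.7%.
- Extension patients, Days 1 to 98: 14/98 = 14.3%. Same windows: 6/94 = 6.4% to 22/102 = 21.6%.

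**From days to events.** The documents give no event rates. As an assumption, let the daily AESI rate off drug be k times the rate on drug. The expected off-drug share of counted events is then k × off / (on + k × off):

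| k | No extension (28 on, 9 off) | Extension part (56 on, 14 off) |
|---|---|---|
| 0.5 | 13.8% | 11.1% |
| 1 | 24.3% | 20.0% |
| 2 | 39.1% | 33.3% |
| 5 | 61.6% | 55.6% |

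**Effect of one patient.** A patient whose only event in a table row is post-treatment adds 1/12 = 8.3 points to a cohort rate and 1/24 = 4.2 points overall. A patient already counted in that row adds nothing, because subjects are counted once per SOC or PT.

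**Scheduled calcium sampling, Days 29 to 98** (Table 4 with its footnotes). There is one sample on each of Days 29, 30, 42, 70, 85, 86 and 98, and three on each of Days 56 and 84: 7 + 6 = 13. Three of the 13 (Days 85, 86 and 98) follow the last dose, or 23%, close to the 20% share of days.

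**Do other tables separate the periods?** The relationship table does not. SAP 17.1.1 counts events judged unlikely to be related as treatment-related, and treats a missing relationship as related. Counting each subject once also means that a patient with the same event on and off drug appears once, with no sign of the period.

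**The case against.** The best case against is that counting follow-up events as treatment-emergent is conservative and not wrong in itself, since withdrawal effects belong in a safety account. AE collection closes the window in practice. The study is open-label, uncontrolled and descriptive. All of this stands, and it is why the definition should stay.

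Some stronger readings are tempting and are not supported:
- *The events cannot be told apart.* They can, by hand. All AEs are listed with an AESI flag. Onset time and supplement amounts are recorded for hypo- and hypercalcemia (Protocol synopsis, Variables), and dosing is listed (SAP 14.0). With about 24 patients this is workable. The gap is in the tables.
- *Detection is concentrated after the last dose.* Three of nine scheduled calcium days suggests so, but 3 of 13 samples does not. The checks required within 5 days of any AZP-3601 adjustment add further on-drug sampling.
- *The titration-feasibility conclusion is biased.* Nothing ties feasibility to an AESI rate. Dose changes, serum calcium and supplement use are summarized separately, and no direction of bias can be shown.
- *A 24-hour cut-off is the natural one.* SAP 7.1 expects quick elimination, but that concerns plasma drug. No text shows that the calcium effect ends within a day, and Day 85 would sit at that boundary.

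It is also fair that a split would not isolate the drug effect, because supplements change during dosing too. That limits what the on-treatment column can show. It does not justify adding the withdrawal period to it.

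**Conclusion.** The point holds as a cheap improvement to the tables, not as an error in the TEAE definition or a loss of data. As described, the AESI tables combine on-drug events with events from an interval in which the drug is stopped and supplements are resumed. That interval is 24% of collection days for patients who do not continue, 20% of the extension part, and 14% of the whole study for patients who do. How many events this involves is unknown; the range above rests on the assumed k. The 24% applies only to patients who decline the extension, and their number is not given.

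Two further limits apply. The SAP gives no rule for assigning an AE to main or extension, so placing follow-up events in the part just completed is an inference. The table shells (SAP Appendix 4) and the full protocol body are not in the text reviewed, so a by-period layout or a TEAE window there cannot be ruled out, although SAP 3.0 says that the SAP supersedes the protocol's statistical considerations.

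**What to change.** Keep the TEAE definition. In SAP 17.1.1:
- Add on-treatment and post-treatment columns, by onset relative to the last dose, to the TEAE and AESI tables, by cohort and for main and extension.
- Prespecify the cut-off and justify it from the PK and serum calcium data; do not adopt 24 hours by default.
- State the part to which follow-up events belong.
- Report both columns. Base statements about AESIs on AZP-3601 on the on-treatment column, with the caveat that supplements also change during dosing. Describe the post-treatment column as the withdrawal and supplement-resumption period.

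The split uses onset and dosing dates and needs no new data collection or change to patient management. The cost is slightly longer tables with small post-treatment counts.
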